- C9. ‘Creatine supplementation and placebo control’ will consist of an initial loading dose (see consent) of 10g/day for 5 days and then a daily 5g/day for 4 weeks. All creatine and placebo powders will be given in containers marked with a date for consumption and serving spoon and instruction guide. All creatine will be purchased from a local nutrition store (General Nutrition Center, GNC). All cellulose will be purchased from an online supplement store (Allergy Research Group, ARG). Subject instructions for taking the supplement will be provided to them and are attached to this submission.
- Subjects’ visits (after screening visit) are planned for baseline (Visit 2) and Day 28 (Visit 3). However, due to scheduling

PROTOCOL TITLE: Creatine supplementation and muscle stretching in peripheral artery disease patients

conflicts that are likely to arise, if a subject cannot come back on Day 28, there will be a 5-day study visit window (+/-) to allow for scheduling but not acquire protocol deviations. Stretching and supplementation will continue to occur during that time. Any study visit outside of this extended visit window will be documented as a deviation. Finally, any subject/patient that doesn't adhere to a "no alcohol for 24h or food/caffeine 4h" prior to testing will be rescheduled for another later date.

6.3 Describe:

Specific risks:

Healthy control subjects and peripheral artery disease patients: uncomfortable muscle stretch and blood pressure cuff. Fitbit may cause skin irritation.

Placebo: uncomfortable muscle stretch, blood pressure response to walking. Bloating, gas, diarrhea from fiber pill.

Creatine: uncomfortable muscle stretch, blood pressure response to walking. Bloating, gas, diarrhea, muscle cramping during creatine supplementation. We are unaware of any further risks with creatine supplementation.

We will reduce risk of patients with a standardized protocol across all subjects. For example, we will maintain weekly contact with the patients both inside the laboratory and while at home with phone calls and messages. In addition, the cardiologist's knowledge of the patient will provide us with the information to include or exclude the patient. During the most vigorous task (six-minute walk test) we will place chairs along the hallway in case the patient gets too tired to continue and can rest until they are recovered.

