9.3 We anticipate complete primary analysis by summer 2021

10.0 Inclusion and Exclusion Criteria*

PROTOCOL TITLE: Creatine supplementation and muscle stretching in peripheral artery disease patients

10.1 The inclusion criterion for the PAD study group is a resting ankle-brachial index (ABI) of 0.90 or less in either leg or clinical diagnosis by a medical doctor. All patients must have a stable condition for at least 3 months. Subjects in the healthy volunteer group do not need to meet the PAD inclusion criteria.

- Subjects must be ages 40 - 95
- PAD patients will be screened/cleared to participate by their primary care physician cardiologist and then by our research team. Healthy volunteers do not require physician clearance to participate.
- All subjects must have the ability to speak and read English to be included in this study.

10.2 Subjects (PAD and healthy controls) are excluded according to whether they meet one or more of the following criteria:

- habitual exercise or cardiovascular rehabilitation program during the past 3 months
- below or above-knee amputation, critical limb ischemia (ulceration or gangrene)
- leg pain at rest
- major surgery or lower extremity revascularization during the previous 3 months
- major medical illness treatment during the prior 12 months
- central neurological disease
- limited ankle or knee joint range of motion
- requirement of oxygen with activity or exercise
- Any New York Heart Association level of heart failure
- atrial fibrillation
- wheelchair confinement, or inability to walk
- cognitive disorder
- vasculitis problem including Takayasu's arteritis, Berger's disease, collagen disease or Raynaud's disease
- Subjects whose physician feels that participation in this research project would not be appropriate for him/her will be excluded.
- overt cardiovascular disease
- metabolic disease
- renal disease

Exclusion specific to the MRI: If patients have any history of pacemakers or pacer wires, open heart surgery, artificial heart valves, aneurysm clips, cochlear implants, braces or extensive dental work, implanted electrical or mechanical devices, tissue expanders, foreign metallic objects from explosives, shrapnel or metalwork fragments, or artificial limbs. Subjects will also be excluded if they are pregnant, claustrophobic, have tremors or cannot lie still for 1-2 hours.

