12.0 Local Number of Subjects

12.1 *The goal of this study is to enroll 20 individuals with PAD and 20 healthy volunteers. To account for screenfails and withdrawals, we will enroll up to 50 subjects in this study.*

12.2 *N/A*

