17.0 Data Management* and Confidentiality

17.1 *Statistical analysis will include repeated measures ANOVA with Bonferroni post hoc analysis and paired samples t-test when applicable. Due to the nature of the current investigation (pilot study) we will be running a power analysis once the data set is collected.*

17.2 During this study, and after consent is obtained, medical history questionnaires will be filled out prior to the start of the study. Experimental measurements will be obtained for statistical analyses and for research purposes only, and data will be kept in strict confidence. No information will be given to anyone without written permission from the subject. Data will be entered into REDCap and stored in a HIPAA compliant environment. Confidentiality will be ensured by use of identification codes. All data, whether generated in the laboratory or in post-processing will be identified with an identification code unique to the subject. The master identification code list will be kept under lock and key access limited to the P.I. and necessary members of the study team. Any presentation or publication of the data will be done in cumulative fashion without identifiers.

17.3 *Our protocols include standard operating procedures for calibration of instrumentation and all data collection.*

17.4 *Describe how data or specimens will be handled study-wide:*

- *All data collected on paper will be identified only by subject ID. Paper forms will be entered and/or uploaded into REDCap database which only the research team will have access to. Subject contact information will be necessary, but this information will be stored separately with limited access to the study team members who must contact the subjects for AE tracking and appointment reminders.*

PROTOCOL TITLE: Creatine supplementation and muscle stretching in peripheral artery disease patients

- Individual participant paper files will be stored in a locked cabinet in a locked office only accessible to the research team. Any data extracted from the REDCap database will be secured with password protection. Electronic communication between investigators will only involve anonymous information.

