Cover Page

Study Title: Creatine Use and Muscle Stretching in Peripheral Artery Disease

NCT Number: NCT04471792

Date of Statistical Analysis Plan: 04-02-2022

Statistical Analysis Plan to follow

PAD- Stretching +Creatine Statistical Analysis

The primary goal of this study is to determine the effects of splint-based passive muscle stretching with and without creatine monohydrate supplementation protocol on changes in microvascular function, walking performance, and subjective measures of walking performance in PAD patients. Based on data from Moraes et al. [129] who reported a 10% increase in post-occlusive reactive hyperemia in participants taking creatine (effect size: 0.78, mean 1: 0.54, mean 2: 0.49, pooled SD 0.02), a sample size of 9 participants per group was needed to detect changes in microvascular reperfusion variables with 80% power and an α of 0.05. Descriptive statistics were calculated for all variables and included means and standard deviations for normally distributed continuous variables and medians, minima and maxima for non-normally distributed continuous variables. Independent t-tests were used to determine if there were differences in baseline variables between groups. If baseline values between groups were significantly different, a secondary analysis was conducted using an analysis of covariance with baseline values as covariates. If sphericity was violated ($\varepsilon < 1$), a Greenhouse-Geisser correction was used. Changes in dependent variables over time were analyzed using repeated measures ANOVA (group by time). When interactions were significant, independent and paired t-tests were used to determine where differences were located. If there were no differences in measured variables between creatine and placebo supplementation, data were pooled, and paired t-tests were used to evaluate pre to post differences in the measured variables of microvascular function, walking performance, and subjective measures of walking performance. Pearson Product Moment Correlations were completed on baseline variables to look at relationships between microvascular function, walking performance, and subjective measures of walking performance. All significance was accepted at $p < 0.05$. Statistical outliers were removed if they exceeded 2 standard deviations from the baseline mean or mean changes from pre to post-intervention. All analyses were performed using the SPSS 27 statistical package.

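### The creatine-versus-placebo test ignores baseline unless a baseline t-test is significant, and the SAP does not say which result prevails

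*SAP*

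**What the plan says.** The SAP is a single section. Its only unconditional between-arm test of the intervention is this one: "Changes in dependent variables over time were analyzed using repeated measures ANOVA (group by time". Baseline is handled separately: "Independent t-tests were used to determine if there were differences in baseline variables between groups". Adjustment then depends on that result: "If baseline values between groups were significantly different, a secondary analysis was conducted using an analysis of covariance with baseline values as covariates".

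The between-arm result also decides what happens next: "If there were no differences in measured variables between creatine and placebo supplementation, data were pooled", after which pre-to-post paired t-tests are run on the combined arms. The SAP does not name the analysis that settles whether there were no differences.

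Protocol section 17.1 has no baseline adjustment: "Statistical analysis will include repeated measures ANOVA with Bonferroni post hoc analysis and paired samples t-test when applicable". Protocol section 6.2 sets one measurement before and one after the intervention; visits after screening "are planned for baseline (Visit 2) and Day 28 (Visit 3".

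The SAP does not label any test as primary. Calling the group-by-time ANOVA the main test is an inference from its being unconditional and from the ANCOVA being called secondary.

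**The concern.** Creatine versus placebo is the randomised comparison, and the arms are very small. Three things are unsatisfactory.

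- **Efficiency.** A change score subtracts the whole baseline value, whatever the correlation between visits. ANCOVA estimates how much to subtract. Unless the correlation is high, the change score is the noisier estimate.
- **The trigger.** Under randomisation, a baseline p-value does not measure whether an imbalance matters for the estimate. In small arms it misses moderate imbalances that still shift the change estimate.
- **No precedence rule.** Where the ANCOVA is run, there are two p-values for one question and no sentence saying which is reported as the treatment effect or which governs pooling. That leaves a choice to be made after the data are seen, where the change test is least reliable.

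Because a non-significant comparison leads to pooling, lost power also makes pooling over a real difference more likely.

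**Working it through.** **Inputs.** From the SAP: 9 per group, 80% power, alpha 0.05 (two-sided assumed), effect size 0.78, means 0.54 and 0.49, pooled SD 0.02. From Protocol 12.1: "The goal of this study is to enroll 20 individuals with PAD and 20 healthy volunteers", so about 10 PAD patients per arm if the split is equal (the ratio is not stated). The pre/post correlation ρ is in neither document and is varied from 0.3 to 0.9. Data are taken as normal with equal SD at both visits, and 0.78 is read as SDs of a single measurement.

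**The plan's own figure.** For two independent groups, n = 2 × (1.96 + 0.84)² / 0.78² ≈ 26 per group (27 by the t distribution), not 9. The stated means and SD give (0.54 − 0.49)/0.02 = 2.5 SD, which needs 3 to 4 per group. So 9 is not reproduced by either route. That is a separate issue; both effect sizes are carried below.

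**Step 1: what the main test is.** With two time points, the group-by-time F equals the squared t for the difference in mean change. On a generated data set both came to 1.955, p = 0.181.

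**Step 2: when the baseline test fires.** The observed gap must reach t(0.975, 16) × √(2/9) = 2.12 × 0.471 = 1.00 SD. The gap between two arms of 9 has SD 0.471, so it exceeds 0.5 SD in either direction in about 29% of trials (0.5/0.471 = 1.06). Removing the roughly 5% that are flagged leaves 24% unflagged, which simulation confirms.

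**Step 3: efficiency, bias and disagreement.** The large-sample variance ratio of ANCOVA to change is (1 + ρ)/2. At 9 per arm, estimating the slope multiplies it by about 15/14. Given a baseline gap g (creatine minus placebo), the change estimate is off by −(1 − ρ) × g, and ANCOVA by about 0. The ratios and powers below come from 200,000 simulated trials per setting. Disagreement comes from 900,000 per ρ, of which about 45,000 were flagged.

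| ρ | Variance ratio | Power, change | Power, ANCOVA | Bias of change, g = +0.5 SD | Verdicts differ when flagged |
|---|---|---|---|---|---|
| 0.3 | 0.70 | 26% | 35% | −0.35 SD | 38% |
| 0.5 | 0.81 | 34% | 41% | −0.25 SD | 36% |
| 0.7 | 0.91 | 52% | 56% | −0.15 SD | 33% |
| 0.8 | 0.96 | 69% | 70% | −0.10 SD | 27% |
| 0.85 | 0.99 | 81% | 81% | −0.075 SD | 22% |
| 0.9 | 1.02 | 94% | 93% | −0.05 SD | 13% |

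- At ρ = 0.5, the change test needs about 11 per arm to match ANCOVA at 9 (both 41%). With 10 per arm, power is 38% versus 46%.
- Unflagged gaps above 0.5 SD with creatine higher occur in 12% of trials and average 0.68 SD. At ρ = 0.5 the bias is then −0.5 × 0.68 = −0.34 SD.
- If the effect is really 0.78 SD and ρ = 0.5, the comparison is non-significant, and the arms would be pooled, in 100 − 34 = 66% of trials under the change test and 100 − 41 = 59% under ANCOVA.

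**Step 4: error rates.** Over all trials both methods have mean error 0.00 SD and type I error of about 5%. Among null trials with a flagged baseline, the change test rejects in 23%, 17%, 11% and 8% at ρ = 0.3, 0.5, 0.7 and 0.9; ANCOVA rejects in about 4% to 5%. Counting either result as a success gives 5.0% to 5.3% overall. With several independent baseline variables, the chance that at least one is flagged is 1 − 0.95^k: 14%, 23% and 40% for k = 3, 5 and 10.

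**Step 5: the other effect size.** At 2.5 SD, power is 98.7% (change) versus 99.9% (ANCOVA) at ρ = 0.3, and at least 99.9% for both from ρ = 0.5 upward.

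**The case against.** The strongest reply is that the plan is not invalid. A change-score comparison is a legitimate estimator, and calling the ANCOVA secondary already implies an order. The disagreement rates apply only to the 5% or so of comparisons that are flagged. As a share of all comparisons they are 0.05 × 38%, 36%, 33% and 13%, or about 1.9%, 1.8%, 1.6% and 0.7% at ρ = 0.3, 0.5, 0.7 and 0.9, with almost no inflation of type I error per endpoint. The power gain depends on an unknown correlation and on how 0.78 is read. Where the gain is largest, ANCOVA still reaches only 35% to 41%, so the shortage of power is mainly a sample-size problem.

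Most of this stands and limits the weight of the point. It does not remove it. An implied order is not a rule for discordant results, and it does not say which test governs pooling. If the ANOVA does prevail, the conclusion rests on the less reliable test exactly when imbalance has been detected.

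Two points of reading are fair. The SAP provides a Greenhouse-Geisser correction, which has no role with two time points; the visit schedule and the paired pre-to-post tests support the two-level reading. The SAP also does not say whether each endpoint's own baseline triggers its own ANCOVA. The 5% rate assumes that it does; a trigger on any variable would fire more often.

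The simulations assume normal data and do not include the SAP's removal of values beyond 2 SD. Pooling after a non-significant result is a defect in its own right and adds nothing to the weight given here.

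**Conclusion.** The concern holds. The only unconditional between-arm test is an unadjusted change comparison. ANCOVA depends on a significant baseline test, and no rule settles conflicts or the pooling decision.

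At 9 per arm and an effect of 0.78 SD, the change test gives up about 9, 7 and 4 points of power at correlations of 0.3, 0.5 and 0.7, 1 point at 0.8, and nothing from 0.85. At 2.5 SD the power argument disappears. The bias given an observed imbalance does not depend on the effect size: a quarter of an SD at correlation 0.5 for a gap of 0.5 SD, half the size the baseline test can detect.

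This should be changed because the remedy costs almost nothing. It does not make the existing test invalid.

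**What to change.** 1. Make ANCOVA the main creatine-versus-placebo analysis for every endpoint: post value on arm, with that endpoint's own baseline as covariate, reported as the adjusted difference with a 95% confidence interval.
2. Drop baseline significance tests as a trigger and report baseline values descriptively.
3. Keep the group-by-time ANOVA as supportive. State that ANCOVA prevails if the two differ, including wherever the plan refers to a difference between arms.
4. State how the adjusted model treats non-normal endpoints and whether the 2 SD outlier rule applies before it.

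The cost is SAP wording and one SPSS model per endpoint, on data already collected. ANCOVA uses one degree of freedom and loses under 1 point of power near a correlation of 0.9.

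Timing matters. Protocol 9.3 says "We anticipate complete primary analysis by summer 2021", and the SAP is dated 2022 and written in the past tense. If results had been seen before the change, report ANCOVA for all endpoints beside the analysis as planned and label it post hoc.

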To reduce the risk of skin irritation associated with the Fitbit, all subjects will be instructed to keep the device clean, dry, and to not wear the device too tightly. If skin irritation occurs and does not resolve within 3 days, subjects will be instructed to discontinue use of the device. If any soreness, tingling, numbness, burning, or stiffness in the hands occurs in the hands or wrists, subjects will be instructed to discontinue use of the device immediately. To reduce risk of the above, subjects will be given the following instructions:

1. Do not attempt to replace the battery, open the enclosure or disassemble your Fitbit product.
2. Do not use your Fitbit product if the display is cracked.
3. Do not expose your Fitbit product to extremely high or low temperatures.
4. Do not use your Fitbit product in a sauna or steam room.

PROTOCOL TITLE: Creatine supplementation and muscle stretching in peripheral artery disease patients

5. Do not use abrasive cleaners to clean your Fitbit product.
6. Remove your Fitbit product immediately if it feels warm or hot.
7. Charge the battery with the charging cable provided. Do not use other cables.
8. Do not wear your Fitbit product while charging it.
9. Do not charge your Fitbit product while it is wet.

Creatine monohydrate will be used in the current investigation. The purpose of using creatine is to create a favorable metabolic environment to improve patients' ability to walk.

- The use of creatine monohydrate in this investigation has been approved by the FDA.

The source records that will be used to collect data about subjects are attached to the IRB submission and will be kept in a locked cabinet in a locked office.

6.4 All data will be collected by trained members of the study team (NIRS, MRI, blood pressure, heart rate, anthropometry, Fitbit, and cardiovascular (i.e., six-minute walk test) variables.

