15.2 N/A

15.3 N/A

15.4 N/A

16.0 Potential Benefits to Subjects*

16.1 Benefits

Healthy control: None.

Placebo: increasing functional capacity and cardiovascular health outcomes.

Creatine: increasing muscle blood flow, increasing functional physical capacity and cardiovascular health outcomes.

Static muscle stretching has been shown to improve muscle blood flow. We believe that combining creatine supplementation with muscle stretching will enhance the efficacy of the treatment protocol, further enhancing cardiovascular function.

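### Pooling creatine and placebo after a non-significant test at 9 per arm lets a low-power test decide whether the arm-specific changes, which are the primary goal, are tested at all

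*SAP*

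**What the plan says.** The SAP opens with its aim: "The primary goal of this study is to determine the effects of splint-based passive muscle stretching with and without creatine monohydrate supplementation". It plans a group-by-time repeated measures ANOVA. After a significant interaction it runs independent and paired t-tests to locate the differences. Otherwise: "If there were no differences in measured variables between creatine and placebo supplementation, data were pooled, and paired t-tests were used" on microvascular function, walking performance and subjective walking measures. The only decision threshold is "All significance was accepted at" p < 0.05. There is no equivalence margin and no confidence-interval criterion. The SAP does not say whether the absence of differences is judged per variable or across all of them, or how the pooled change will be interpreted.

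On size, the SAP says "a sample size of 9 participants per group was needed to detect changes in microvascular reperfusion variables with 80% power". Protocol section 17.1 names repeated measures ANOVA, Bonferroni post hoc tests and paired t-tests, and has no pooling rule.

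The protocol gives mixed signals on where creatine should act. The formal hypothesis (section 2.2) ties it to phosphorus metabolites and ties oxygenation and blood flow to stretching. Section 5.1, however, makes walking distance an objective for the combination. Section 6.3 says "The purpose of using creatine is to create a favorable metabolic environment to improve patients' ability to walk", and section 16.1 expects that "combining creatine supplementation with muscle stretching will enhance the efficacy of the treatment protocol".

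**The concern.** A non-significant test in a small trial says little about whether two arms are alike. Here that result does two things: it switches off the arm-specific paired tests and puts one averaged test in their place. The primary goal asks about each regimen, and the average describes neither unless creatine does nothing.

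Every randomised subject stretches (protocol section 6.1), so a significant pooled gain is easily summarised as a benefit of stretching. If creatine had an effect that the trial missed, part of it would then be credited to stretching. Walking is one of the pooled domains, and the protocol expects creatine to help it, so this possibility is not remote.

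**Working it through.** **The plan's own figure.** The SAP gives an effect size of 0.78, means of 0.54 and 0.49, a pooled SD of 0.02, 80% power and α = 0.05, and concludes 9 per group. This was not reproduced on a standard reading.
- A two-sample t-test at 0.78 SD needs 27 per group two-sided, or 22 one-sided. A paired test needs 15 or 12.
- The means and SD give (0.54 − 0.49)/0.02 = 2.5 SD, which contradicts 0.78 and needs 4 per group.
- Two unstated readings come close, each giving 8 per group: 0.78 taken as Cohen's f, or a repeated measures interaction with f = 0.39 and an assumed pre-post correlation of 0.5.

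The check below therefore takes 9 per arm as given and varies the effect.

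**Assumptions.** Equal arms (no allocation ratio is stated), two-sided test at 0.05, equal SDs, SD of change = 1, pooling decided by the between-arm test on change, one outcome at a time, no outlier removal.

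**1. What a non-significant result leaves open.** The 95% half-width for the between-arm difference is t(0.975, 16) × √(2/9) = 2.120 × 0.471 = 1.00 SD of change. Power reaches 80% only at 1.41 SD.

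**2. How often the arms are pooled.** This is the noncentral t probability of p ≥ 0.05 with 16 degrees of freedom and noncentrality d × √(9/2).

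| Assumed creatine effect d (SD of change) | Arms pooled |
|---|---|
| 0 | 95% |
| 0.3 | 91% |
| 0.5 | 83% |
| 0.78 | 66% |
| 1.01 | 48% |
| 1.23 | 31% |
| 1.74 | 7% |
| 2.5 | 0.1% |

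The values 0.3 and 0.5 are assumptions. Putting 0.78 on the change scale is also an assumption: if it is in raw SD units, the effect on change is 0.78/√(2(1 − ρ)), where ρ is the pre-post correlation. That equals 0.78 at ρ = 0.5, and 1.01, 1.23 and 1.74 at ρ = 0.7, 0.8 and 0.9. The documents give no ρ.

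**3. What the pooled change estimates.** Let s be the stretch-only change and s + d the change with creatine. With equal arms the pooled mean is (s + s + d)/2 = s + d/2. In simulation with s = 0, the mean pooled change in pooled trials was 0.15, 0.25 and 0.39 SD at d = 0.3, 0.5 and 0.78. At d = 0.78 the pooled paired test was significantly positive in 31% of pooled trials, although stretching alone did nothing.

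**4. Is this due to the condition or to averaging?** At d = 0.3/0.5/0.78, the pooled 95% interval covers the stretch-only change in 91/84/69% of pooled trials. Pooling always, with no condition, gives 91/85/71%. The interval covers the average over arms in 95–96% of pooled trials. So the shortfall comes from averaging, and the ANOVA time effect shares it.

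**5. Sensitivity.**
- At 10 per arm (20 PAD patients in protocol section 12.1, equal split assumed), pooling occurs in 90.3/81.5/62.1% of trials at 0.3/0.5/0.78 SD.
- If three independent outcomes must all be non-significant, it falls to 75/57/28%.
- With the SAP's 2-SD outlier rule it is 87/79/63% (applied within arm) or 92/85/71% (applied across arms).

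**The case against.** The strongest defence is that nothing essential is lost. The group-by-time ANOVA is run first, so the randomised comparison stands and pooling is a follow-on analysis. The pooled change is a valid average, and the SAP never calls it the effect of stretching alone. All of this is right, and it limits the point to how the pooled result is read and to what is left untested.

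Scale also matters. If 0.02 is taken as the SD of change, the half-width is 0.02 × 1.00 = 0.02, and a non-significant result would roughly exclude the 0.05 difference for that one variable. So a reader might infer that non-significance can never be informative here, and that goes too far. The exception rests on a 2.5 SD effect that contradicts the SAP's own 0.78, and the walking and questionnaire outcomes have no power basis.

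Three other stronger readings are not supported:
- *The condition itself spoils the pooled interval.* Step 4 shows that averaging does this, with or without the condition.
- *Conditional pooling is a worse estimator whatever the effect.* Against either fixed rule (always pool, or always use the placebo arm) the result is mixed, and choosing the better fixed rule requires knowing the effect.
- *A creatine effect on every pooled outcome is the formal hypothesis.* Section 2.2 assigns phosphorus metabolites to creatine, and these are not among the SAP's named pooled domains. The expectation for walking and function comes from sections 5.1, 6.3 and 16.1.

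**Conclusion.** The point holds in a limited form. With p < 0.05 as the only criterion and 9 per arm, non-significance generally does not show that creatine and placebo are alike. Pooling would be common for small to moderate creatine effects (91% of trials at 0.3 SD of change, 66% at 0.78), less so for large ones (31% at 1.23, 7% at 1.74), and harmless if creatine has no effect. The fault of the rule is that a low-power test decides whether the arm-specific changes are tested at all. The half-share of any creatine effect in the pooled change is a property of averaging.

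The sizes rest on equal allocation, 9 analysed per arm and assumed effects on the change scale. The logical point needs none of these. This is an inexpensive improvement to reporting and does not threaten the randomised comparison.

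**What to change.** Remove the significance condition for pooling. For every outcome, whatever the test result, report:
1. the creatine-minus-placebo difference in change with its 95% confidence interval, as the randomised comparison;
2. each arm's pre-to-post change with its 95% confidence interval, labelled as change from baseline without a randomised no-stretch control. The 2–4 PAD time controls in protocol section 6.2 (item C2) are too few to serve as one and do not appear in the SAP analysis.

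Do not infer a creatine effect by comparing the two within-arm p-values. A pooled change or the ANOVA time effect may still be shown if labelled as the average over the creatine and placebo arms, all stretching.

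An equivalence test in place of the condition would not help at this size. With zero true creatine effect, 9 per arm would show equivalence within assumed margins of 0.5, 0.78 or 1.0 SD in only 0.1, 7 or 31% of trials.

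The cost is SAP wording and reporting, with no new data. The loss is precision: the average half-width for the stretch-only change is about 0.75 SD against 0.50 pooled, a ratio of 1.5. For estimating the stretch-only change, the pooled mean has the smaller mean squared error when d²/4 + 1/18 < 1/9, that is, when d is below 2√(1/18) = 0.47 SD. That is a reason to keep a labelled average alongside the arm-specific results.

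### The SAP's 2 SD deletion rule, applied to the pre-post change itself, lifts the pooled paired t-test's type I error from 5% to about 8-10% (whole-sample cutoffs) or 7-8% (per-arm cutoffs)

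*SAP*

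**What the plan says.** The SAP's single analysis section gives the rule in one sentence: "Statistical outliers were removed if they exceeded 2 standard deviations from the baseline mean or mean changes from pre to post-intervention". Distance from a mean is the only criterion. The SAP does not say whether the mean and SD come from the whole sample or from each arm, which SD applies to the change cut, or whether the rule is applied once.

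The tests it feeds are a repeated measures ANOVA ("Changes in dependent variables over time were analyzed using repeated measures ANOVA (group by time") and a conditional pre-post test. "If there were no differences in measured variables between creatine and placebo supplementation", then "data were pooled, and paired t-tests were used to evaluate pre to post differences". Significance is taken at p < 0.05 throughout. The planned size is given as "a sample size of 9 participants per group was needed", "with 80% power and an α of 0.05".

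The only secondary analysis is for baseline imbalance: "a secondary analysis was conducted using an analysis of covariance with baseline values as covariates". It is not an analysis with the outlying values restored. Protocol section 17.1 names the ANOVA and paired t-tests but has no outlier rule and no full-data analysis.

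**The concern.** A 2 SD cut is not a rare safeguard. With clean normal data at 9 per group and nothing wrong with any measurement, about 81% of trials lose at least one patient on a given variable under whole-sample cutoffs, and about 54-55% under per-arm cutoffs.

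The cut on change matters most. Change is what the paired t-test and the group-by-time test analyse. Removing its tails and then computing an ordinary standard error understates the spread, so p-values come out too small.

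The SAP's primary goal covers what stretching does alone and together with creatine, over microvascular, walking and self-reported outcomes. When the arms do not differ, the pooled paired test is how the SAP judges pre-post change in all patients together. A nominal 5% test that really runs at 7-10% can change which outcomes are reported as improved, and nothing planned would show the reader that this had happened.

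**Working it through.** **Inputs from the SAP:** 9 per group (18 pooled), α 0.05, the 2 SD rule on baseline and on change, the pooled paired t-test and its pooling condition. **Assumed, because the documents are silent:** two-sided tests; equal arms; one pass; a patient's pair is dropped for the variable concerned; the change cut uses the SD of change; pre-post correlation 0.5 to 0.9; the data shapes below.

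**The plan's own figures.** The 9 per group does not follow from the stated inputs ("effect size: 0.78, mean 1: 0.54, mean 2: 0.49, pooled SD 0.02"): (0.54 − 0.49)/0.02 = 2.5, not 0.78. A two-sided two-sample t-test needs 27 per group at 0.78 and 4 at 2.5; a paired test at 0.78 needs 15. A total of 18 can be reached with a repeated measures interaction at f = 0.39 and correlation 0.4, but neither is stated. Here 9 serves only as the planned n. The α of 0.05 is reproduced when nothing is deleted: the pooled paired t-test rejects in 4.98% of null trials with normal data.

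**Rule as simulated.** With d = post − pre, drop the pair if |pre − mean(pre)| > 2·SD(pre) or |d − mean(d)| > 2·SD(d). Then run a one-sample t-test on all remaining d (the pooled paired test) and a two-sample t-test on d by arm (identical to group-by-time with two time points). There were 100,000 trials per setting (simulation error about 0.1 point), correlations 0.5 and 0.8. The other shapes are t with 4 df, lognormal with sigma 0.5, and normal with 5% of post values given extra error of SD 3.

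| Type I error at 9 per group | Untrimmed | Whole-sample cutoffs | Per-arm cutoffs |
|---|---|---|---|
| Pooled pre-post test, normal data | about 5% | 9.8-10.2% | 7.8-8.1% |
| Pooled pre-post test, other shapes | 4.0-5.1% (all shapes) | 8.0-9.1% | 7.1-7.9% |
| Group-by-time test | 4.1-5.0% | 4.9-5.2% | 7.5-8.4% |

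A separate set of 400,000 trials per setting, normal data, correlations 0.5 to 0.9, gave 9.7-10.1% and 7.7-8.0% for the pooled test. Restricting to trials with a non-significant group test, as the SAP's pooling condition does, moved these by about 0.1 point or less.

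**Which cut does it.** Normal data, pooled test: baseline cut alone 5.2-5.9%; change cut alone 7.7-10.0%. The SD of change falls on average by about 11% (whole-sample) or 5-6% (per-arm).

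**Check by hand** (normal data, change cut only, whole-sample, large n). Let P = Pr(|Z| ≤ 2) = 0.9545 and φ(2) = 0.0540.
- Variance of the kept values: (P − 4φ(2))/P = 0.7385/0.9545 = 0.774, so the SD is 0.88 of its true value.
- Squared standard error that the t-test uses: 0.774/P = 0.811 (per n).
- True variance of the trimmed mean, allowing for the cutoffs moving with the sample mean: [0.7385·(1 + 8φ(2)) + (4φ(2))²]/P² = 1.212 (per n).
- The t statistic is inflated by √(1.212/0.811) = 1.22, so 1.96 acts as 1.96/1.22 = 1.60, a two-sided error of about 10.9%.

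The simulated 9.8-9.9% for the same cut at 18 pooled patients, and 10.4% at 40, approach this limit.

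**If the change cut used the baseline SD instead:** type I error of the pooled test is about 10% at correlation 0.5, about 6% at 0.8 and about 5% at 0.9.

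**Dependence on n.** At 10 per arm (the 20 PAD patients of Protocol section 12.1, split equally): 10.0-10.2% whole-sample, 8.2-8.3% per-arm. The greatest possible distance from a group's own mean is (n − 1)/√n SDs: 2.67 at n = 9, but 1.79 at n = 5. Per-arm cutoffs therefore remove nothing at 5 or fewer per arm.

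**Effect on a true creatine difference.** Whole-sample cutoffs turn 0.78 SDs of change into 0.67-0.70. A difference of 2.5 outcome SDs becomes 2.39-2.49. Per-arm cutoffs leave the estimate unchanged.

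**The case against.** The best defence is that the rule is numeric and leaves little room for case-by-case deletion, that this is a pilot, and that the firmest harm falls on a conditional pre-post test without a concurrent comparison. A correct 5% level there would still not show that stretching worked, since any change over time counts as a rejection. The pooled test is also not the only look at change over time: the repeated measures ANOVA has a time effect. All of this is fair and limits the weight of the point. It does not restore the level: a rule followed exactly breaks the SAP's own p < 0.05, the ANOVA runs on the same trimmed data, and the rule leaves its cutoff basis open.

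The SAP also expects some non-normal variables. That lowers the whole-sample figure to 8-9% but does not remove the excess.

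Three stronger readings are tempting and are not supported:
- A reader might infer that the error rate doubles whatever the data. About 10% is the normal-data, whole-sample figure only.
- A reader might infer that the randomised creatine comparison is prone to false positives. That holds only with per-arm cutoffs, which the SAP does not state; with whole-sample cutoffs it stays near 5%.
- A reader might infer a loss of power. With whole-sample cutoffs and 0.78, power moves between −7 and +6 points depending on the scale of the effect and the data shape.

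**Conclusion.** The rule is wrong as written. At 9 per group the pooled pre-post test has a type I error of about 8-10% with whole-sample cutoffs or 7-8% with per-arm cutoffs, instead of 5%. This rests on two-sided tests, one pass, pairwise removal per variable, and a change cut on the SD of change, which is the natural reading. On the less natural reading with the baseline SD, the excess depends on a pre-post correlation that the documents do not give and nearly vanishes at 0.9.

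For the group-by-time test, one of two consequences follows, not both: type I error of about 7.5-8.5% (per-arm), or a level near 5% with an estimate drawn towards zero (whole-sample), materially so at 0.78 change-SDs and much less for larger effects. The documents do not show which applies.

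**What to change.** Make the analysis of all valid observations primary, with the same models. Exclude a value only for a documented measurement or recording fault, and list each exclusion with its arm and reason. Report any 2 SD-trimmed run only as a labelled sensitivity analysis that states the cutoff basis (whole sample or per arm, and which SD) and that the rule is applied once.

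The cost is revised SAP wording and a re-run of the same models; no new data are needed. Pooled pre-post p-values will on average be slightly less favourable: with normal data, whole-sample cutoffs and no true change, the median p is about 0.50 on full data against 0.42 trimmed. The group-by-time result will also look less favourable on average if cutoffs were per arm. If they were whole-sample it may move either way: at 0.78 change-SDs, median p on full data against trimmed is 0.11 against 0.14-0.15 for normal data, and 0.10-0.11 against 0.09 for skewed data.
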